9.4 Adverse Event Reporting

9.4.1 IRB Reporting Requirements:

The UNC-IRB will be notified of all SAEs that qualify as an Unanticipated Problem as per the UNC IRB Policies using the IRB's web-based reporting system within 7 days of the Investigator becoming aware of the problem. Please note, these events must be reported to the sponsor within 24 hours of learning of the occurrence.

Multicenter sites:

- For multicenter sites using a local IRB of record, please submit adverse events per local IRB policy.
- For multicenter sites relying on the UNC-IRB, an aggregated list of any SAEs that qualify as an Unanticipated Problem will be entered into OnCore® by the multicenter site and reported to the UNC IRB by the Multicenter Regulatory Associate using the IRB's web-based reporting system within 7 days of the Investigator becoming aware of the problem.

Pregnancy

Pregnancies and suspected pregnancies (including a positive pregnancy test regardless of age or disease state) of a female subject occurring while the subject is on study, or within 30 days of the subject's initial dose of study drug and prior to post-treatment surgery should be recorded as SAEs. The subject is to be discontinued immediately from the study.

The female subject should be referred to an obstetrician-gynecologist, preferably one experienced in reproductive toxicity for further evaluation and counseling.

For multicenter sites, the pregnancy, suspected pregnancy, or positive pregnancy test must be reported to the Multicenter Project Manager immediately (within 24 hours) via email. The Multicenter Project Manager will then report the event to

the Funding Source (see requirements below). The female subject should be referred to an obstetrician-gynecologist, preferably one experienced in reproductive toxicity for further evaluation and counseling.

The Investigator will follow the female subject until completion of the pregnancy and must document the outcome of the pregnancy (either normal or abnormal outcome). If the outcome of the pregnancy was abnormal (e.g., spontaneous or therapeutic abortion), the Investigator should report the abnormal outcome as an AE. If the abnormal outcome meets any of the serious criteria, it must be reported as an SAE.

9.4.2 Merck Reporting Requirements:

Also refer to Appendix 5, as needed.

9.4.2.1 Adverse Events (AEs), Serious Adverse Events (SAEs), and Other Reportable Safety Events

The definitions of an AE or SAE, as well as the method of recording, evaluating, and assessing causality of AE and SAE and the procedures for completing and transmitting AE, SAE, and other reportable safety event reports can be found in Appendix F.

Adverse events, SAEs, and other reportable safety events will be reported by the participant (or, when appropriate, by a caregiver, surrogate, or the participant's legally authorized representative).

The investigator and any designees are responsible for detecting, documenting, and reporting events that meet the definition of an AE or SAE as well as other reportable safety events. Investigators remain responsible for following up AEs, SAEs, and other reportable safety events for outcome.

The investigator, who is a qualified physician, will assess events that meet the definition of an AE or SAE as well as other reportable safety events with respect to seriousness, intensity/toxicity and causality.

9.4.2.2 Time Period and Frequency for Collecting AE, SAE, and Other Reportable Safety Event Information

All AEs, SAEs, and other reportable safety events that occur after the consent form is signed but before intervention allocation/randomization must be reported by the investigator if the participant is receiving placebo run-in or other run-in treatment, if the event cause the participant to be excluded from the study, or is the result of a protocol-specified intervention, including but not limited to washout or discontinuation of usual therapy, diet, or a procedure.

- All AEs from the time of intervention allocation/randomization through 30 days following cessation of study intervention must be reported by the investigator.
- All AEs meeting serious criteria, from the time of intervention allocation/randomization through 90 days following cessation of study intervention or 30 days following cessation of study intervention if the participant initiates new anticancer therapy, whichever is earlier, must be reported by the investigator.
- All pregnancies and exposure during breastfeeding, from the time of intervention allocation/randomization through 120 days following cessation of study intervention, or 30 days following cessation of study intervention if the participant initiates new anticancer therapy must be reported by the investigator.
- Additionally, any SAE brought to the attention of an investigator at any time outside of the time period specified above must be reported immediately to Merck if the event is considered drug-related.

Investigators are not obligated to actively seek AEs or SAEs or other reportable safety events in former study participants. However, if the investigator learns of any SAE, including a death, at any time after a participant has been discharged from the study, and he/she considers the event to be reasonably related to the study intervention or study participation, the investigator must promptly notify Merck.

All initial and follow-up AEs, SAEs, and other reportable safety events will be recorded and reported to Merck within the time frames as indicated in the table below.

Reporting Time Periods and Time Frames for Adverse Events and Other Reportable Safety Events

Type of Event	Reporting Time Period: Consent to Randomization/ Allocation	Reporting Time Period: Randomization/ Allocation through Protocol- specified Follow- up Period	Reporting Time Period: After the Protocol- specified Follow-up Period	Time Frame to Report Event and Follow-up Information to Merck:
Serious Adverse Event (SAE) including Cancer and Overdose	Report if: - due to protocol- specified intervention - causes exclusion - participant is receiving placebo run-in or other run- in treatment	Report all	Report if: - drug/vaccine related. (Follow ongoing to outcome)	Within 2 business days but no longer than 3 calendar days of learning of event
Pregnancy/Lactation Exposure	Report if: - due to	Report all	Previously reported – Follow to	Within 2 business days

CONFIDENTIAL

January 9, 2025

Type of Event	Reporting Time Period: Consent to Randomization/ Allocation	Reporting Time Period: Randomization/ Allocation through Protocol- specified Follow- up Period	Reporting Time Period: After the Protocol- specified Follow-up Period	Time Frame to Report Event and Follow-up Information to Merck:
	intervention - causes exclusion		completion/termination; report outcome	but no longer than 3 calendar days of learning of event
Event of Clinical Interest (require regulatory reporting)	Report if: - due to intervention - causes exclusion	Report - potential drug- induced liver injury (DILI) - require regulatory reporting	Not required	Within 2 business days but no longer than 3 calendar days of learning of event

9.4.2.3 Method of Detecting AEs, SAEs, and Other Reportable Safety Events

Care will be taken not to introduce bias when detecting AEs and/or SAEs and other reportable safety events. Open-ended and nonleading verbal questioning of the participant is the preferred method to inquire about AE occurrence.

9.4.2.4 Follow-up of AE, SAE, and Other Reportable Safety Event Information

After the initial AE/SAE report, the investigator is required to proactively follow each participant at subsequent visits/contacts. All AEs, SAEs, and other reportable safety events including pregnancy and exposure during breastfeeding, events of clinical interest (ECIs), cancer, and overdose will be followed until resolution, stabilization, until the event is otherwise explained, or the participant is lost to follow-up. In addition, the investigator will make every attempt to follow all nonserious AEs that occur in allocated or randomized participants for outcome. Further information on follow-up procedures is given in Appendix F.

9.4.2.5 **Sponsor Responsibility for Reporting Adverse Events**

All Adverse Events will be reported to regulatory authorities, IRB/IECs and investigators in accordance with all applicable country specific regulatory requirements, global laws and regulations.

9.4.2.6 **Pregnancy and Exposure During Breastfeeding**

Although pregnancy and infant exposure during breastfeeding are not considered AEs, any pregnancy or infant exposure during breastfeeding in a participant (spontaneously reported to the investigator or their designee) that occurs during the study are reportable to Merck.

LCCC 1827 PI: [name], MPH Amendment 6

All reported pregnancies must be followed to the completion/termination of the pregnancy. Pregnancy outcomes of spontaneous abortion, missed abortion, benign hydatidiform mole, blighted ovum, fetal death, intrauterine death, miscarriage, and stillbirth must be reported as serious events (Important Medical Events). If the pregnancy continues to term, the outcome (health of infant) must also be reported.

9.4.2.7 Events of Clinical Interest (ECIs)

Selected nonserious and SAEs are also known as ECIs and must be reported to Merck.

Events of clinical interest for this study include:

- 1. An overdose of pembrolizumab that is not associated with clinical symptoms or abnormal laboratory results. For purposes of this study, an overdose of pembrolizumab will be defined as any dose of 1,000 mg or greater (≥5 times the indicated dose). No specific information is available on the treatment of overdose of pembrolizumab. In the event of overdose, the participant should be observed closely for signs of toxicity. Appropriate supportive treatment should be provided if clinically indicated. If an adverse event(s) is associated with ("results from") the overdose of a Merck product, the adverse event(s) is reported as a serious adverse event, even if no other seriousness criteria are met.
- 2. An elevated AST or ALT lab value that is greater than or equal to 3X the upper limit of normal and an elevated total bilirubin lab value that is greater than or equal to 2X the upper limit of normal and, at the same time, an alkaline phosphatase lab value that is less than 2X the upper limit of normal, as determined by way of protocol-specified laboratory testing or unscheduled laboratory testing.*

*Note: These criteria are based upon available regulatory guidance documents. The purpose of the criteria is to specify a threshold of abnormal hepatic tests that may require an additional evaluation for an underlying etiology.

9.4.3 Syndax Reporting Requirements

The investigator must inform Syndax in writing using a SAE form or MedWatch 3500A form of any SAE within 24 hours of being aware of the event. The date of awareness should be noted on the report. The written report must be completed and supplied to Syndax within 24 hours at the latest on the following working day. The initial report must be as complete as possible, including details of the current illness and (serious) adverse event, and an assessment of the causal relationship between the event and the investigational product(s). Information not available at the time of the initial report (e.g., an end date for the adverse event or laboratory values received after the report) must be documented on a follow-up report. A final report to document resolution of the SAE is required.

Completed SAE Report Forms should be emailed to: [contact]

or

Back-up method only: fax to [name]

9.5 FDA Expedited Reporting Requirements for Studies Conducted Under an IND

A sponsor must report any suspected adverse reaction that is both serious and unexpected to the FDA. The sponsor must report an adverse event as a suspected adverse reaction only if there is evidence to suggest a causal relationship between the drug and the adverse event, such as:

- A single occurrence of an event that is uncommon and known to be strongly associated with drug exposure (e.g., angioedema, hepatic injury, Stevens-Johnson Syndrome);
- One or more occurrences of an event that is not commonly associated with drug exposure, but is otherwise uncommon in the population exposed to the drug (e.g. tendon rupture);
- An aggregate analysis of specific events observed in a clinical trial (such as known consequences of underlying disease or condition under investigation or other events that commonly occur in the study population independent of drug therapy) that indicates those events occur more frequently in the drug treatment group than in a concurrent or historical control group.

The sponsor must submit each IND safety report on FDA Form 3500A. Each notification to FDA must bear prominent identification of its contents, i.e., "IND Safety Report," and must be transmitted to the review division that has the responsibility for review of the IND. In each IND safety report, the sponsor must identify all IND safety reports previously submitted to FDA concerning a similar suspected adverse reaction and must analyze the significance of the suspected adverse reaction in light of previous, similar reports or any other relevant information.

Timing

FDA must be notified of potential serious risks within 15 calendar days after the sponsor determines the event requires reporting. FDA must be notified of unexpected fatal or life-threatening suspected adverse reactions as soon as possible but in no case later than 7 calendar days after the sponsor's initial receipt of the information. The sponsor must be notified of the SAE by the investigator within 24 hours of the event. If the results of a sponsor's investigation show that an adverse event not initially determined to be reportable is reportable, the sponsor must report such suspected adverse reaction in an IND safety report as soon as possible, but in no case later than 15 calendar days after the determination is made.

Follow-up

The sponsor must promptly investigate all safety information it receives. Relevant follow-up information to an IND safety report must be submitted as soon as the information is available and must be identified as such, i.e., "Follow-up IND Safety Report." Additionally, upon request from FDA, the sponsor must submit to FDA any additional data or information that the agency deems necessary, as soon as possible, but in no case later than 15 calendar days after receiving the request.

Notification of Investigators

The sponsor must notify all participating investigators (i.e., all investigators to whom the sponsor is providing drug under its INDs or under any investigator's IND) in an IND safety report of potential serious risks, from clinical trials or any other source, as soon as possible, but in no case later than 15 calendar days after the sponsor determines that the information qualifies for reporting.

Process

If the sponsor deems that an event is both a serious adverse reaction (SAR) AND unexpected, it must also (in addition to OnCore®) be recorded on the MedWatch Form 3500A as per 21 CFR 312.32. Unexpected adverse events or adverse reaction refers to an event or reaction that is not listed in the investigator's brochure or is not listed at the specificity or severity that has been observed; or if an investigator's brochure is not required or available, is not consistent with the risk information described in the general investigation plan or elsewhere in the current IND application.

The MedWatch form should be submitted on MedWatch by the study coordinator.

The MedWatch 3500A form can be accessed at: http://www.fda.gov/Safety/MedWatch/HowToReport/DownloadForms/default.htm.

(Please be sure and access form 3500A, and not form 3500 or 3500B).

The MedWatch form should also be sent to the UNC Regulatory Associate and the IND Specialist within 48 hours of the sponsor being aware of the event. The Regulatory Associate with the aid of the IND Specialist will submit the IND Safety Report via IND serial submission to the FDA review division.

All IND safety reports must be submitted on Form 3500A and be accompanied by Form 1571. The FDA must be notified or any unexpected or life-threatening suspected adverse reactions as soon as possible, but no later than 7 calendar days of learning of the event.

Additional Reporting Requirements

The following additional items must be reported via IND safety report:

• Findings from other studies. The sponsor must report any findings from epidemiological studies, pooled analysis of multiple studies, or clinical studies, whether or not conducted under an IND, and whether or not

- conducted by the sponsor, that suggest a significant risk to humans exposed to the drug.
- Findings from animal or in vitro testing. The sponsor must report any findings from animal or in vitro testing, whether or not conducted by the sponsor, that suggest a significant risk in humans exposed to the drug, such as reports of mutagenicity, teratogenicity, or carcinogenicity, or reports of significant organ toxicity t or near the expected human exposure.
- *Increased rate of occurrence of serious suspected adverse reactions.*

Additional Guidance

Please refer to 21CFR312.32 and "Guidance for Industry and Investigators: Safety Reporting Requirements for INDs and BA/BE Studies" for additional information and reporting requirements. All IND Safety Reports will be submitted in accordance with these regulations/guidances.

9.6 Data and Safety Monitoring Plan

The Principal Investigator will provide continuous monitoring of subject safety in this trial with periodic reporting to the Data and Safety Monitoring Committee (DSMC).

Meetings/teleconferences will be held at a frequency dependent on study accrual. These meetings will include the investigators as well as protocol nurses, clinical research associates, regulatory associates, data managers, biostatisticians, and any other relevant personnel the principal investigators may deem appropriate. At these meetings, the research team will discuss all issues relevant to study progress, including enrollment, safety, regulatory, data collection, etc.

The team will produce summaries or minutes of these meetings. These summaries will be available for inspection when requested by any of the regulatory bodies charged with the safety of human subjects and the integrity of data including, but not limited to, the oversight (Office of Human Research Ethics (OHRE) Biomedical IRB, the Oncology Protocol Review Committee (PRC) or the North Carolina TraCS Institute Data and Safety Monitoring Board (DSMB).

The UNC LCCC Data and Safety Monitoring Committee (DSMC) will review the study on a regular (quarterly to annually) basis, with the frequency of review based on risk and complexity as determined by the UNC Protocol Review Committee. The UNC PI will be responsible for submitting the following information for review: 1) safety and accrual data including the number of subjects treated; 2) significant developments reported in the literature that may affect the safety of participants or the ethics of the study; 3) preliminary response data; and 4) summaries of team meetings that have occurred since the last report. Findings of the DSMC review will be disseminated by memo to the UNC PI, PRC, and the UNC IRB and DSMB.

10.0 STATISTICAL CONSIDERATIONS

10.1 Study Design/Study Endpoints

Our statistical design is based on a primary endpoint of the change in T cell immune gene signature with treatment. Based on studies in our lab that analyzed changes in immune gene signature expression with chemotherapy in pre-treatment TURBT and post-treatment surgery specimens, we hypothesize a change in Z-score of the T cell immune gene signature of approximately 0.5 with pembrolizumab alone with a standard deviation of 0.49, and a similar change with the addition of entinostat compared to pembrolizumab alone.

10.2 Sample Size, Accrual and Duration of Accrual

We will accrue 10 subjects in each of the two study arms to detect a difference in change in expression using a two group t-test with 80% power and a one-sided alpha of 10% (will accrue N=20 total, 10 subjects in each arm). The hypothesized mean change is 0.5 in the pembrolizumab alone arm and 1.0 in the entinostat +pembrolizumab arm, and we assume a 0.49 common standard deviation.

After 5 subjects that undergo subsequent trimodality therapy are accrued to the study, the number of post-treatment surgery samples that were collected will be reviewed by the study team to ensure that adequate tumor sampling has occurred in this subset of subjectss. It will then be decided to continue the study allowing the inclusion of trimodality subjects (if post-treatment surgical sample collection was adequate) or restrict further accrual to cystectomy subjects only.

Accrual will take place over two years.

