3.0 STUDY ENDPOINTS

3.1 Primary Endpoint

Change in immune gene signature expression will be defined based on change in the T cell immune gene signature from mRNAseq analysis in the pembrolizumab + entinostat group compared to the pembrolizumab alone group

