3.2 Secondary Endpoints

- **3.2.1** Pre- and post-treatment TCR repertoire and neoantigen changes will be defined by changes in TCR clonality and neoantigen load.
- 3.2.2 Pre- and post-treatment changes in STAT and NF-κB expression will be evaluated using mRNAseq analysis and changes in histone acetylation (H3K9Ac and H3K27Ac) levels in a subset of subjects with pre- and post-treatment tumor tissue available (diagnostic TURBT and maximal TURBT or cystectomy tissue available)
- 3.2.3 Toxicity will be evaluated according to guidelines from National Cancer Institute

 Common Terminology for Adverse Events (NCI-CTCAE) criteria version 5.0
 and include all adverse events continuing or occurring 30 days after completion of treatment
- **3.2.4** A pathologic response will be defined as <pT2 (pT0-T1N0M0) and pathologic complete response will be defined as pT0N0M0 at the time of cystectomy at the completion of study treatment.
- 3.2.5 The clinical complete response rate (cT0) is defined as cT0 at the time of maximal TURBT
- **3.2.6** EFS is defined as day 1 of neoadjuvant/protocol treatment to date of first documentation of disease progression (or until recurrence after surgery or radiation) or death due to any cause. Recurrence includes the development of second primary muscle-invasive urothelial malignancies.
- **3.2.7** Overall survival is defined as day 1 of neoadjuvant/protocol treatment to date of death due to any cause. Patients will be censored at date of last follow-up.

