4.1 Inclusion Criteria

- **4.1.1** Written informed consent obtained to participate in the study and HIPAA authorization for release of personal health information.
- 4.1.2 Subjects must agree to donate tumor tissue from their diagnostic transurethral resection of the bladder tumor (TURBT) and from their post-treatment surgery (cystectomy or repeat maximal TURBT). Subjects must also agree to donate whole blood prior to initiating therapy, during study therapy and at post-treatment surgery.
- **4.1.3** Age \geq 18 years at the time of consent.
- **4.1.4** Eastern Cooperative Oncology Group performance status of ≤ 2 .
- **4.1.5** Histological confirmation of urothelial carcinoma of the bladder; those with mixed histology, including a component of urothelial carcinoma, are eligible. Pure small cell carcinoma, pure adenocarcinoma, and pure squamous cell carcinoma are excluded.
- **4.1.6** Subject has clinical stage T2-T4a N0/X M0 urothelial carcinoma. Clinical T stage is based on the pre-study standard of care transurethral resection of the bladder tumor (TURBT) sample and imaging studies (abdominal/pelvic CT or MRI scan and CT scan of the chest performed within 4 weeks prior to treatment initiation).
- **4.1.7** Available formalin-fixed paraffin-embedded (FFPE) archival tumor specimen that contains sufficient tissue to generate at least 15 (preferably 20) unstained slides, each with tissue sections that are 5 10 microns thick.
- **4.1.8** Subject is planned to undergo definitive therapy for MIBC with either surgery (radical cystectomy) or trimodality therapy (including repeat TURBT followed by concurrent chemoradiation). Subjects undergoing trimodality therapy must be deemed to not be a candidate for radical cystectomy, or refuse radical cystectomy. Suggested chemotherapy regimens are outlined in Appendix E but not mandated by protocol.
- **4.1.9** Subject demonstrates adequate organ function as defined in the table below; all screening laboratory assessments should be performed within 10 days of treatment initiation.

System	Laboratory Value
--------	------------------

Hematological	
Absolute neutrophil count (ANC)	$\geq 1.5 \times 10^{9}/L$
Platelets	≥100 × 10 ⁹ /L
Hemoglobin	≥9 g/dL
Renal	
Estimated GFR per CKD-EPI equation	≥30 mL/min
Hepatic	
Serum total bilirubin	≤ 1.5 mg/dL (subjects with Gilbert's syndrome may be enrolled despite a total bilirubin level >1.5 mg/dL if their conjugated bilirubin is <1.5 × ULN)

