7.3 Correlative Studies Procedures

7.3.1 Archival Tumor Tissue

Archived primary tumor in fixed paraffin-embedded blocks or slides from the diagnostic TURBT specimen of each subject must be requested at baseline for correlative studies. Additionally, we will request banked tissue on the subset of patients who have previously had tissue frozen via UNC's Tissue Procurement Facility's standing collection protocol, or through our group's biospecimen repository protocol (LCCC1212).

mRNA Sequencing and Gene Expression Profiling

RNA will be extracted from tumor samples, libraries will be prepared using the TruSeq RNA Access protocol. mRNA libraries will be sequenced, and relevant gene expression signatures will be evaluated, including relative expression of preand post-treatment STAT3 and NF- κ B signatures, IFN γ -related genes, MHC class I/II genes, and immune checkpoint genes and other immune gene signatures.

Immunohistochemistry

Histone acetylation (H3K9Ac and H3K27Ac) levels will be assessed via immunohistochemistry.

Whole Exome Sequencing

DNA will be extracted and whole-exome sequencing libraries will be generated. Exome sequence data will be processed using the established pipeline developed at UNC. Buccal swabs will be used as a source for normal DNA.

ChIP-Sequencing

For the subset of patients with frozen diagnostic TURBT and post-treatment surgical tissue available, we will perform ChIP-sequencing for H3K27Ac and other histone markers (H3K4Me3 and K3K27Me3, etc.) to assess where changes in histone post-translational modifications associate with active transcription.

T Cell Receptor Repertoire Profiling: immunoSEQ Assay
TCR repertoire amplification and sequencing will be done on tumor and
peripheral blood samples after DNA extraction. The TCRb CDR3 regions will be
amplified and sequenced using immunoSEQ. Pre- and post-treatment TCR
repertoire clonality will be compared to assess for an antigen-specific immune
response.

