10.3 Data Analysis Plans

The change in T cell gene signature expression will be calculated for each group (pembrolizumab + entinostat compared to pembrolizumab alone) and compared between groups using a two group t-test. Similar analyses will be done for all gene signatures.

Appropriate descriptive statistics, including median, interquartile range, means, and 95% confidence intervals, will be calculated and reported for all lab values.

The analysis of the toxicity and safety will be based on the frequency of adverse events and their severity. Worst toxicity grades per subject will be tabulated for adverse events and laboratory measurements by using the National Cancer Institute- Common Terminology Criteria for Adverse Events (NCI-CTCAE version 5.0) and will be reported in the form of frequency tables. If 2 subjects have their surgical resection delayed beyond the 10 weeks from the time of initiation of study therapy due to protocol treatment-related adverse events, further enrollment to the study will be halted. Based on the nature and severity of

LCCC 1827 PI: [name], MPH Amendment 6 CONFIDENTIAL UNIVERSITY OF NORTH CAROLINA January 9, 2025

the toxicities observed, consideration will be made to amend the study (if risk of toxicity is felt to be mitigated by protocol amendment) vs terminating the study. If 4 or more patients are delayed due to protocol treatment-related adverse events, then the study will be terminated.

For subjects that undergo cystectomy, the proportion of patients who have a pathologic response to <pT2 will be reported along with a 95% confidence interval. Similarly, the proportion of patients who have a clinical complete response (cT0) will be reported separately for those undergoing cystectomy and trimodality therapy. Patients who progress prior to surgery (unlikely) or do not have surgery will still be included in this estimate and will be considered to have not been downstaged. The Kaplan Meier method will be used to estimate median times, along with 95% confidence intervals, for the secondary objectives of EFS and OS, as defined in Section 3.2.6 and 3.2.7.

Results gathered on these subjects will be highly valuable in providing information that can be used to inform power and sample size considerations for future investigations.

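### Does the 80% power in section 10.2 fail because it is tied to accrued subjects and not to usable pre/post tumor pairs?

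*Combined protocol and SAP*

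**What the plan says.** Section 10.2 attaches the power to accrual: "We will accrue 10 subjects in each of the two study arms to detect a difference in change in expression". It assumes a mean change of 0.5 with pembrolizumab alone and 1.0 with the combination, a common standard deviation of 0.49, 80% power and a one-sided alpha of 10%.

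Section 3.1 defines the primary endpoint through "change in the T cell immune gene signature from mRNAseq analysis". Section 7.3.1 gives the source material: "RNA will be extracted from tumor samples, libraries will be prepared using the TruSeq RNA Access protocol". Section 10.1 bases the planning values on earlier laboratory work on changes measured "in pre-treatment TURBT and post-treatment surgery specimens". Section 10.3 compares the change between arms with a two-group t-test.

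On tissue supply, section 4.1.2 makes donation an entry condition: "Subjects must agree to donate tumor tissue from their diagnostic transurethral resection of the bladder tumor (TURBT) and from their post-treatment surgery". Section 4.1.7 requires enough archival tissue for at least 15 slides. Sections 5.8 and 8.2 ask subjects who withdraw or stop treatment early for specimens at surgery. Section 10.2 adds a review of post-treatment sample collection after 5 trimodality subjects, which may restrict later accrual to cystectomy subjects.

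The documents give no rate of unusable samples, no inflation of accrual, no target for evaluable pairs and no replacement rule.

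**The concern.** A change score needs two measurements. A subject without usable tumor RNA at either time has no change score and drops out of the primary t-test, yet section 10.2 counts accrued subjects as if all of them will be analysed.

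Some loss is foreseeable. Complete response is itself an endpoint: in section 3.2, "pathologic complete response will be defined as pT0N0M0 at the time of cystectomy", and clinical complete response is assessed in trimodality subjects. A bladder without residual tumor may yield no tumor RNA. Section 10.3 also provides for subjects who never reach surgery: "Patients who progress prior to surgery (unlikely) or do not have surgery will still be included in this estimate". That sentence settles how they count for response, but nothing settles how a missing pair is treated in the primary test.

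If several pairs were lost, the power would fall below 80%, and a reader who took 80% as holding for 20 accrued subjects could read too much into a negative result. Section 10.3 also says the results will be "used to inform power and sample size considerations for future investigations", so it is fair to ask which N the power refers to.

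**Working it through.** **Inputs** (section 10.2): difference in mean change δ = 1.0 − 0.5 = 0.5; SD σ = 0.49; one-sided α = 0.10; 10 subjects per arm.

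**Formula.** For n₁ and n₂ usable pairs, the standard error is σ·√(1/n₁ + 1/n₂), the noncentrality is δ divided by that standard error, and df = n₁ + n₂ − 2. Power is the probability that a noncentral t variable exceeds the upper 10% point of the central t.

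**Reproducing the plan's figure.** With 10 per arm:
- standard error = 0.49 × √0.2 = 0.219
- noncentrality = 0.5 / 0.219 = 2.28
- df = 18, critical value 1.330
- power = 82.8%

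Nine per arm gives 79.6%, so 10 is the smallest equal-arm size that reaches 80% by the exact test. The normal approximation gives 84.1% at 10 and 81.1% at 9. The stated sample size is therefore right for 10 usable pairs per arm.

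**Power when pairs are lost** (same formula):

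| Usable pairs per arm | Pairs lost of 20 | Power |
|---|---|---|
| 10 / 10 | 0 | 82.8% |
| 10 / 9 | 1 | 81.2% |
| 9 / 9 | 2 | 79.6% |
| 10 / 8 | 2 | 79.2% |
| 9 / 8 | 3 | 77.6% |
| 10 / 7 | 3 | 76.8% |
| 8 / 8 | 4 | 75.7% |
| 10 / 6 | 4 | 73.7% |
| 7 / 7 | 6 | 71.3% |
| 10 / 4 | 6 | 64.9% |

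With two pairs lost the shortfall is 80 − 79.6 = 0.4 points or 80 − 79.2 = 0.8 points. Under the normal approximation both cases stay above 80% (81.1% and 80.8%). With four lost, the shortfall is 4.3 points if the loss is balanced and 6.3 if it falls on one arm. With six lost, it is 8.7 and 15.1.

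**Average power under random loss.** The rates are assumed, since the documents give none. Averaging over two independent binomial counts of usable pairs gives 81% at 5% loss, 79% at 10%, 75% at 20% and 70% at 30%.

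**Detectable difference at 80% power:** 0.48 with 10 pairs per arm, 0.50 with 9, 0.54 with 8 and 0.58 with 7.

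**Comparison with another planning uncertainty.** If no pair is lost but the SD is 0.55 instead of 0.49, the standard error is 0.55 × √0.2 = 0.246, the noncentrality is 2.03 and the power is 75.9%. That is about the cost of losing four pairs evenly (75.7%). The 0.49 comes from specimens of patients given chemotherapy (section 10.1), not either study regimen, so an error of this size in the SD cannot be ruled out.

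**The case for a change.** The strongest case for acting is that the point is true and cheap to mend. The power does depend on pairs, the slack is about one pair in 20, and the sponsor's own review of trimodality sampling shows that yield was in doubt. The safeguards reduce loss but do not replace a lost pair or raise N. The archival-tissue rule protects only the pre-treatment sample, and the trimodality review covers one subset with no numeric threshold. Two added sentences would make the power conditional at no cost to patients.

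All of that stands as description, but it does not amount to a defect that needs correcting:

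- No stated figure is wrong, and the 80% holds to within one point with two pairs lost.
- A larger shortfall needs three or more lost pairs. The main route to that, complete responders yielding no usable RNA, is an inference that no section states. The 29% pathologic complete response rate in section 1.3.2 belongs to another agent.
- Rates written into section 10.2 would be invented, and random loss would be the wrong model for that route. Loss through complete response depends on outcome and may differ by arm, so the main question would be which patients the comparison describes. The power averages do not answer it.

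The primary objective in section 2.1 mentions blood as well as tumor. Sections 7.3.1 and 10.1 point to tumor for the mRNAseq signature, so this only slightly qualifies the premise that a pair must be a tumor pair.

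**Conclusion.** No change to the plan follows. Section 10.2 is correct for 10 usable pre/post pairs per arm (82.8% against a stated 80%). The gap is an unwritten assumption that accrued subjects will be evaluable. An analyst would handle it without instruction, by running the t-test on the pairs available and reporting how many there were in each arm and why any were lost. Those observed counts, and the observed SD, are what a later study would plan from.

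The size depends on a loss rate that the documents do not give. It is negligible for one or two pairs of 20. It is about 4 to 9 points below 80% for four to six pairs lost evenly, and about 6 to 15 points if the same losses fall in one arm. These figures assume the planned difference of 0.5 and SD of 0.49, and that loss is unrelated to the change score. Rewording the power statement would alter no accrual, test or conclusion.
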